2.1.1.6 Study day

The study day for all assessments (both efficacy and safety) will be calculated as the difference between the date of the event (visit date, onset date of an event, assessment date, etc.) and the start date of study treatment plus one day. The first day of study treatment is therefore study day 1. The study day for all pre-treatment assessments will be calculated as the difference between the date of the event and the start of study treatment. The last day prior to study treatment intake is therefore Study Day -1.

Unless specified otherwise, the study day will be displayed in the data listings.

2.1.1.7 Baseline

Baseline (e.g. for laboratory parameters), is considered as the last available assessment or value before start of the first treatment, unless otherwise stated under the related assessment. For all relevant parameters comparisons against baseline will be presented through the report.

Baseline could be within 21 days before first treatment administration or on the same day as first treatment administration if specified pre-dose. Specific assessments may be performed more than 21 days prior to day 1 of dosing. Such cases will also be considered as baseline, if no other assessments are performed thereafter, prior to day 1 of dosing. Patients with no data on a particular parameter before the first treatment administration will be considered to have a missing baseline for this parameter.

For ECG evaluations three serial 12-lead ECGs will be obtained on Cycle 1 Day 1 (C1D1) for each patient, prior to the first administration of study drug. The average of the triplicate ECG measurements will serve as the patient's baseline value for post-dose comparisons.

General guidance for baseline definition:

Dependent on the variable, the baseline assessment will be done at screening (Day -21 to 1) or baseline (Cycle 1 Day 1 [C1D1]). Baseline assessments should be obtained before the first study treatment intake based on the variables. Any assessment which is obtained outside of the protocol-defined screening period will not be considered for baseline unless otherwise specified.

2.1.1.8 On-treatment assessment/event and observation periods

The overall observation period will be divided into three mutually exclusive segments:

1. *Pre-treatment period:* from day of patient's informed consent to the day before first administration of study drug
2. *On-treatment period:* from day of first administration of study drug to 30 days after last administration of study drug (Note: for ongoing patients, from day of first administration of study drug to the analysis cut-off date)
3. *Extended safety follow-up period:* from day 31 to at least day 150 after last administration of study drug or lost to follow-up.

In particular, summary tables for adverse events (AEs) will summarize only on-treatment events, with a start date during the on-treatment period, the so-called treatment-emergent AEs.

All safety data (including those from the pre-treatment and extended safety follow-up period) will be listed and those collected during the pre-treatment and extended safety follow-up period are to be flagged.

Additional summaries will be displayed to report deaths, all AEs, AEs related to study treatment, all SAEs and SAEs related to study treatment collected up to 150 days after last administration of study drug.

2.1.1.9 Year, month and week

For reporting purpose below mentioned rule will be followed to convert a year, month and week in days.

1 year = 365.25 days

1 month = 30.3475 days

1 week = 7 days

2.2 Analysis sets

2.2.1 Full analysis set

The Full Analysis Set (FAS) will include all patients who have received at least one dose of study treatment. FAS will be used for the analysis of efficacy endpoints.

If a patient does not have any post-baseline assessment that patients will not be included in FAS.

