Depending on whether or not pre-specified criteria for stopping (for futility) or continuing enrollment (for early success) is met, each tumor cohort can enroll a minimum of 5 patients and a maximum of 30 patients during the course of the study. When at least 5 patients within a group have completed 24 weeks of treatment and have CBR data available, analysis for futility and early success (expansion) will commence to inform a “go/no-go” decision for that cohort. For tumor cohorts in which treatment is not declared futile and pre-specified CBR rate for early success is met, a “go” decision will be made to continue enrolling to a maximum of 30 patients for that cohort. Expanded tumor cohorts will continue to have ongoing analysis for futility to allow for early stopping in the event that observed 24 weeks CBR rates do not meet pre-specified final success criteria (see [Section 10](#)). For tumor cohorts in which treatment has not been declared futile, but criteria for expansion has not been met, enrollment will be paused at 10 patients until a “go/no-go” decision can be made based on information gleaned from the dynamic borrowing of CBR data across tumor cohorts (see [Section 10](#)). A “no-go” decision can be made for a tumor cohort if: 1) 24 week CBR rates of the first 5-10 patients show treatment to be futile and cohort will not expand; 2) subsequent analysis in a cohort that expanded fails to demonstrate continued evidence of activity such that 24 weeks CBR is not predicted to meet pre-specified criteria for final success (See [Section 10](#)).

Primary analysis for all stages will be intent-to-treat. Those patients who discontinue study treatment for any reason other than disease progression or treatment related toxicity may be replaced (at the discretion of Novartis), until at least 5 patients with 24 weeks of CBR data are accrued within a cohort. All patients enrolled into a tumor cohort prior to expansion must not have been exposed to prior immuno-oncology (IO) therapy as specified in exclusion criteria ([Section 5.3](#)).

Once a tumor cohort is selected for expansion, the cohort shall continue to enroll patients until the cohort enrolls a total of 30 patients.

In each expansion cohort, it is permissible to enroll patients that have received previous CPB therapy as follows:

- A maximum of 6 of the 30 patients enrolled into an expansion cohort may have received previous CPB therapy.
- All patients enrolled prior to expansion must be IO naive

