10.1 Analysis sets

10.1.1 Full Analysis Set

The Full Analysis Set (FAS) will include all patients who have received at least one dose of study drug.

FAS will be used for the analysis of efficacy endpoints.

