2.5.3 Handling of missing values/censoring/discontinuations

For the computation of CBR (CR, PR or SD) in case of solid tumor all confirmed responses (CR or PR) reported up to the analysis cut-off will be included. Patients with no valid radiological assessment or unconfirmed responses will be considered as non-responders. In particular, patients with CR or PR at the last radiological assessment prior to cut-off and no response at the previous assessment are by definition unconfirmed and will be considered as non-responders for the primary analysis.

Patients with unknown or missing BOR will be counted as failures (non-responders). If there is no baseline tumor assessment, all post-baseline overall lesion responses are expected to be 'Unknown'. If no valid post-baseline tumor assessments are available, the BOR must be

‘Unknown’ unless progression is reported. For the computation of CBR, these patients will be included in the FAS and will be counted as ‘non-responders’.

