- Progression Free Survival (PFS) defined as the time from the date of first dose to the date of first documented disease progression or relapse or death due to any cause during study medication or within 150 days from last dosing date, and is calculated as $PFS = (\text{date of progression/relapse or death} - \text{date of first study treatment} + 1)$. Disease progression noted as the reason for discontinuation of treatment will also be considered as a progression event for PFS analyses. If a patient has not had an event, progression free survival is censored at the date of last adequate tumor assessment
- Safety and tolerability based on number of incidences of AEs, SAEs, severe AEs, changes in laboratory parameters, vital signs and ECGs, drug interruption, reduction and dose intensity.

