2.7.3 Handling of missing values/censoring/discontinuations

Handling of missing tumor assessments in ORR analysis

For the computation of ORR, in case of solid tumor all confirmed responses (CR or PR) reported up to the analysis cut-off will be included. Patients with no valid radiological assessment or unconfirmed responses will be considered as non-responders. In particular, patients with CR or PR at the last radiological assessment prior to cut-off and no response at the previous assessment are by definition unconfirmed and will be considered as non-responders for the primary analysis.

Patients with unknown or missing BOR will be counted as failures (non-responders). If there is no baseline tumor assessment, all post-baseline overall lesion responses are expected to be 'Unknown'. If no valid post-baseline tumor assessments are available, the BOR must be 'Unknown' unless progression is reported. For the computation of ORR, these patients will be included in the FAS and will be counted as 'failures'.

Censoring rules TTP and PFS calculation

If a patient has not progressed or is not known to have died due to underlying cancer or has received any further anti-neoplastic therapy in the absence of progression, at the analysis cutoff date, will be censored at the date of the last adequate tumor assessment before the cut-off date or before the start of the new anti-neoplastic therapy date, whichever is earlier. Patients who do not have any post-baseline tumor assessment will be considered as censored at Day 1.

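### The SAP drops from the full analysis set some dosed patients whom the protocol and its own CBR and ORR rules keep, and its PFS censoring rule contradicts its PFS definition

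*SAP*

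**What the plan says.** Protocol 10.1.1 defines the analysis set by dosing alone: "The Full Analysis Set (FAS) will include all patients who have received at least one dose of study drug". Protocol 4.3 adds "Primary analysis for all stages will be intent-to-treat".

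SAP 2.2.1 restates the all-dosed definition, assigns the FAS to the efficacy endpoints, and then adds "If a patient does not have any post-baseline assessment that patients will not be included in FAS". The type of assessment is not given. SAP section 4 discloses that the FAS definition was changed and gives only the study team's suggestion as the reason.

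SAP 2.5.3 deals with patients who have no valid post-baseline tumour assessment. Their best response is Unknown unless progression is reported, and "For the computation of CBR, these patients will be included in the FAS and will be counted as" non-responders. SAP 2.7.3 does the same for ORR: "For the computation of ORR, these patients will be included in the FAS and will be counted as" failures.

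For PFS, SAP 2.7.1 counts progression, relapse or "death due to any cause during study medication or within 150 days from last dosing date". It also counts progression given as the reason for stopping treatment. SAP 2.7.3, in one paragraph for TTP and PFS together, opens its censoring condition with "If a patient has not progressed or is not known to have died due to underlying cancer" and ends: "Patients who do not have any post-baseline tumor assessment will be considered as censored at Day 1".

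**The concern.** CBR is the only endpoint tested formally, and each cohort is judged against a fixed historical rate. The first scheduled scan is at week 12. A dosed patient lost before then without a scan is a failure under SAP 2.5.3 but leaves the denominator under SAP 2.2.1 if that section means a tumour assessment. Removing failures can only raise CBR and ORR. The design simulations in Appendix 4 assume no dropouts, so the error rates they report do not cover such losses.

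The PFS problem is separate. The same early death can be an event under one section and censored at Day 1 under another, whichever way 2.2.1 is read.

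**Working it through.** **1. One patient, several rules.** Take a patient who received a dose and has no post-baseline tumour assessment.

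| Source | Treatment of this patient |
|---|---|
| Protocol 10.1.1 and 4.3 | In the FAS |
| SAP 2.2.1, tumour assessment meant | Out of the FAS |
| SAP 2.2.1, any assessment meant | In the FAS if, for example, a post-dose ECG exists |
| SAP 2.5.3 (CBR) and 2.7.3 (ORR) | In the FAS, non-responder |
| SAP 2.7.3 (TTP/PFS) | In the analysis, censored at Day 1 |

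The second row cannot be reconciled with the last two, and the SAP states no order of precedence. Under the any-assessment reading the rows agree for nearly everyone, because Protocol 7.2.2.6.1 schedules ECGs after the first infusion.

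**2. PFS.** Suppose that patient dies of a non-cancer cause in week 8. Under SAP 2.7.1 this is a PFS event at the date of death. Under SAP 2.7.3 it is censored twice over: the death is not from the underlying cancer, and there is no scan. Appendix 1 supports 2.7.1. Section 14.1.19 counts death from any cause, and 14.1.34 uses the start date only where the time is to be censored. The shared paragraph also fails for TTP, because it implies that cancer death is an event while 2.7.1 censors deaths without documented progression.

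**3. Size, simple case.** This applies only if 2.2.1 governs and means a tumour assessment. The inputs are the historical rates R in Appendix 4 Table 1, n = 24 (Appendix 4 section 3), and the exact binomial test at one-sided 0.20 that Appendix 4 section 8 uses as its comparator. The excluded share f is **assumed** at 2%, 5% or 10%, with every excluded patient a failure. For scale, one patient is 1/24 = 4.2% of a full cohort and 1/10 = 10% of a cohort paused at ten.

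The true rate among all dosed patients is set to R, so the rate among those left is R/(1 − f). For gastroesophageal, 43.5/0.98 = 44.4%, 43.5/0.95 = 45.8% and 43.5/0.90 = 48.3%.

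False success = Σ over x ~ Bin(24, f) of P[Bin(24 − x, R/(1 − f)) ≥ k(24 − x)], where k(m) is the smallest count out of m with one-sided p ≤ 0.20 at R.

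| Cohort | f = 0 | 2% | 5% | 10% |
|---|---|---|---|---|
| Gastroesophageal, NET (43.5%) | 0.198 | 0.199 | 0.209 | 0.256 |
| STS (51.1%) | 0.181 | 0.189 | 0.219 | 0.293 |
| Ovarian, DLBCL (25%) | 0.121 | 0.161 | 0.197 | 0.233 |
| SCLC (6.25%) | 0.187 | 0.187 | 0.187 | 0.187 |

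One patient can change a decision under this test. At R = 25%, 8/24 gives p = 0.234 (fails) and 8/23 gives p = 0.196 (passes).

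**4. Size, planned design.** The Appendix 4 design was re-simulated under All Null with:

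- Poisson accrual at the Table 1 rates; first interim at 5 patients with CBR data or 10 enrolled, then every 13 weeks;
- thresholds 0.20, 0.70, 0.60 and 0.80; caps of 10, then 24;
- Dirichlet process with α = 2, truncated at 7 clusters; τ² ~ IG(3, 0.5); μ ~ N(0, 1.82), with 1.82 read as a variance (assumed);
- excluded patients counted to the cap but giving no CBR data at interims or the final analysis.

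There were 800 trials per setting and 1,400 MCMC iterations with 300 burn-in. The Monte Carlo standard error is about 0.01 to 0.02.

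With no exclusion this reproduces the plan: gastroesophageal 0.12 (plan 0.126), any false success 0.43 (0.431), mean trial size 96 (94.3), and mean per-cohort success 0.095 (0.096).

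| Excluded in every cohort | 0 | 2% | 5% | 10% |
|---|---|---|---|---|
| Gastroesophageal | 0.12 | 0.13 | 0.18 | 0.27 |
| SCLC | 0.05 | 0.07 | 0.08 | 0.11 |
| Any false success | 0.43 | 0.48 | 0.56 | 0.68 |
| Any, second run of 400 trials per setting | 0.41 | 0.45 | 0.55 | 0.69 |

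With 10% excluded in gastroesophageal only, that cohort reaches 0.23.

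**The case against.** The best defence is that SAP 2.5.3 is the specific rule for CBR and should prevail over a general sentence. The SAP writes 'tumor assessment' elsewhere when it means one, so in 2.2.1 the unqualified word may mean any assessment. On either argument the effect on CBR and ORR is nil or near nil. This is a fair reading, but not the only one: the exclusion directly follows the statement that the FAS serves the efficacy endpoints, and no precedence is stated.

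SAP 2.5.2 counts progression recorded as the reason for stopping treatment, or as the cause of an on-treatment death, without a scan. That gives many early failures a CBR outcome, but it does not help a patient already removed from the FAS. Protocol 7.2.1 asks for prompt assessment when progression is suspected, which does limit how many patients lack a scan.

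The excluded share is unknown, the larger figures assume the same share in all seven cohorts, and the re-simulation used far fewer MCMC iterations than the plan's 50,000. These limits stand. The SAP Document History mentions one patient left out of an FAS-based protocol deviation report, but gives no reason. That patient may never have been dosed, so the entry does not establish a share.

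PFS is secondary and descriptive, and the Day 1 sentence could be read as applying only to patients who are to be censored anyway. That softens the Day 1 point. It does not remove the conflict over deaths from other causes.

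**Conclusion.** The concern holds, and the text is wrong as written. SAP 2.2.1 departs from the protocol's all-dosed, intent-to-treat set without a substantive reason. If a tumour assessment is meant, it also contradicts SAP 2.5.3 and 2.7.3. The PFS conflict between 2.7.3 and 2.7.1 does not depend on that reading.

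The effect on CBR and ORR is conditional. It is nil or near nil if 2.5.3 governs or any assessment suffices. If 2.2.1 governs with a tumour assessment meant, it is small at 2% excluded and material from about 5%, where any false success under All Null rises from 0.43 to 0.56. Those shares are assumptions, as is the premise that every excluded patient is a failure. It should be corrected regardless, because the denominator of the only tested endpoint, and the event status of early deaths for PFS, each need one definition.

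**What to change.** - **SAP 2.2.1:** delete the exclusion sentence, so that the FAS is all patients with at least one dose, as in Protocol 10.1.1. Amend section 4 to match.
- **SAP 2.5.3 and the ORR rule in 2.7.3:** keep as they are.
- **SAP 2.7.3, TTP and PFS:** separate the two endpoints. For PFS, remove the restriction to cancer deaths, and limit Day 1 censoring to patients with no post-baseline tumour assessment and no PFS event as defined in 2.7.1. Write the TTP rule to agree with 2.7.1.

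The cost is one deleted sentence with its section 4 entry, one reworded paragraph, one population flag and one censoring rule to reprogram. If 2.5.3 was already being followed, CBR and ORR do not change. Otherwise the observed CBR, ORR and PFS results can only stay the same or become less favourable.

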2.2.2 Safety set

The Safety Set will include all patients who received at least one dose of study treatment.

2.2.3 Subgroup of interest

Some specific efficacy analyses will also be repeated in the following subgroup as appropriate. .

1. Tumor cohorts.
2. Prior line of therapy(1,2, and ≥ 3)
3. Number of treatment cycles(less than 3 cycles, ≥ 3 cycles, Less than 5, ≥ 5 cycles)

2.3 Patient disposition, demographics and other baseline characteristics

The FAS will be used for all baseline and demographic summaries and listings unless otherwise specified.

2.3.1 Patient disposition

The following summaries will be provided: % based on the total number of FAS patients:

Treatment phase:

- Number (%) of patients who are still on-treatment (based on the [End of Treatment Phase Disposition] eCRF page not completed);
- Number (%) of patients who have discontinued the study treatment phase (based on the [End of Treatment Phase Disposition] eCRF page);
- Primary reason for study treatment phase discontinuation (based on the [End of Treatment Phase Disposition] eCRF page)
- Number (%) of patients who have entered the post-treatment safety follow-up (based on the [End of Treatment Phase Disposition] eCRF page);
- Number (%) of patients who are still in the post-treatment safety follow-up phase (based on the [End of Post Treatment Phase Disposition] eCRF page not completed);
- Number (%) of patients who have discontinued from the post-treatment follow-up (based on the 'End of Post Treatment Follow-up Disposition' page).
- Reasons for discontinuation from the post-treatment follow-up (based on 'End of Post Treatment Follow-up Disposition' page).

The patient disposition data will be listed for the FAS. All screen failure patients (i.e., patients who discontinued during screening phase) will also be listed along with the relevant information such as reason(s) for screening phase discontinuation.

Protocol deviations

The number (%) of patients with any CSR-reportable protocol deviations (PDs) will be tabulated based on All patients. All protocol deviations will be listed. All PDs will be reviewed during the study and finalized before clinical database lock. All patients will be used to summarize the data.

Analysis sets

The number (%) of patients in each analysis set (defined in [Section2.2](#)) will be summarized and listed .

Patient background, demographics and baseline characteristics

Demographic and baseline characteristics data, disease characteristics, medical history, and prior anti-neoplastic therapies are collected at the screening visit. Descriptive summaries and/or listings will be provided. The FAS analysis set will be used for the summarizing the data. .

Demographic and baseline characteristics

Demographic characteristic variables include:

- Age (years)
- Age category
 - <65 years
 - ≥65 years
 - missing
- Sex
 - Male
 - Female
 - missing
- Race
 - Caucasian
 - Black
 - Asian
 - Native American
 - Pacific Islander
 - Other
 - missing
- Ethnicity
 - Hispanic/latino
 - Chinese
 - Indian
 - Japanese
 - Other east Asian
 - Southeast Asian
 - West Asian
 - Mixed ethnicity
 - Other
 - missing
- Child bearing potential for female patients
 - Able to bear children
 - Premenarche
 - Post menopausal
 - Sterile-of child bearing age

Baseline characteristic variables include:

- Eastern Cooperative Oncology Group - Performance Status (ECOG PS)
 - 0 - Fully active, able to carry on all pre-disease performance without restriction
 - 1 - Restricted in physically strenuous activity but ambulatory and able to carry out work of a light or sedentary nature, e.g., light house work, office work
 - 2 - Ambulatory and capable of all self-care but unable to carry out any work activities. Up and about more than 50% of waking hours

- 3 - Capable of only limited self-care, confined to bed or chair more than 50% of waking hours
- 4 - Completely disabled. Cannot carry on any self-care. Totally confined to bed or chair
- Missing
- Body weight (kg)
- Body height (cm)
- Body surface area (BSA) (m²)
BSA to be calculated as per the DuBois and DuBois formula:
 $= 0.20247 \times \text{height}(\text{m})^{0.725} \times \text{weight}(\text{kg})^{0.425}$
- Cardiac imaging (Left Ventricular Ejection Fraction [LVEF])
- Body mass index(BMI)(kg/m²)
BMI to be calculated as (weight[kg] / (height[m]²) using weight at baseline.

Diagnosis and extent of cancer

Summary statistics will be tabulated for diagnosis and extent of cancer. This analysis will include the following: diagnosis of disease, details of tumor histology/cytology (based on predominant histology/cytology), histological grade, stage at initial diagnosis, time since initial diagnosis to first administration of study drug (in months), time since most recent relapse/progression to first administration of study drug (in months), stage at time of study entry, types of lesions at baseline, and number and type of metastatic sites involved.

Note: Types of lesions at baseline (presence/absence of target and non-target lesions and index and non-index lesions) will be based on the data collected on the [RECIST 1.1 Target Lesion Assessments], [RECIST 1.1 Non-Target Lesion Assessments],[Cheson tumor evaluation - Index lesion] and Cheson tumor evaluation – Non-Index lesion] eCRF pages. Metastatic sites will be based on the [Diagnosis and Extent of Cancer] eCRF page.

Medical history

Medical history and ongoing conditions, including cancer-related conditions and symptoms will be summarized and listed. Separate summaries will be presented for ongoing and historical medical conditions. The summaries will be presented by primary system organ class (SOC) and preferred term (PT). Medical history and current medical conditions will be coded using the Medical Dictionary for Regulatory Activities (MedDRA) terminology. The MedDRA version used for reporting will be specified in the CSR and as a footnote in the applicable tables/listings.

